5.2. Rationale for Protocol Amendment (a)

The I2V-MC-CXAD protocol was amended to make the following changes:

- include FOLFOX as an accepted prior therapy for pancreatic cancer
- allow for enrollment of patients with celiac disease if their disease is controlled only with diet
- add echocardiography at baseline to document initial left ventricular (LV) function. Additionally, echocardiography may be performed on-study as clinically indicated to determine left ventricular ejection fraction (LVEF)/LV dysfunction and any change in cardiac size or function. An echocardiography guidance was included as a protocol attachment ([Attachment 12](#)).
- exclude patients with history of QT interval prolongation, history of uncontrolled cardiac arrhythmias or congenital long QT syndrome, or who require drugs known to cause QT prolongation
- change the exclusion criterion for mean QTc interval from ≥ 470 ms to ≥ 450 ms to align with ICH E14 guidelines
- observe the initial patient in the 40-mg cohort in Phase 1a for 2 weeks, after which additional patients will be enrolled after notification from the sponsor. This allows for a

safety assessment prior to enrolling subsequent patients since this dose level has not previously been investigated.

- clarify that final analysis will be conducted no more than 12 months after the last patient enters treatment
- allow dose interruption up to 12 weeks. Management of immune-mediated adverse events (AEs), including steroid tapering, allows a 12-week window for resolution before discontinuing study treatment.
- add dose-limiting toxicity (DLT) and LY2510924 discontinuation criteria of \geq Grade 3 QT prolongation AE per Common Terminology Criteria for Adverse Events (CTCAE) criteria
- clarify an exclusion to the DLT list. Grade 3 thrombocytopenia not associated with bleeding that requires clinically significant medical intervention and improves by at least 1 grade within 3 days is not considered a DLT.
- clarify LY2510924 dose adjustments, delays, and discontinuations and revise a discontinuation criterion from LY2510924 treatment. Patients with combined elevated aspartate aminotransferase (AST)/alanine aminotransferase (ALT) AND total bilirubin values meeting discontinuation parameters as described in the DLT definition should be considered for permanent discontinuation based on clinical judgment.
- include scheduled electrocardiogram (ECG) assessments to assess QT interval length periodically during study therapy

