Patients who have discontinued from combination treatment will enter the Post Discontinuation Follow-Up Period with visits at approximately 30, 60, and 90 days. If a patient has discontinued treatment for reasons other than disease progression, tumor assessments should continue every 8 weeks until confirmed disease progression occurs, initiation of a new anticancer therapy, the patient dies, or is lost to follow-up. Patients will be followed for survival at least every 12 weeks (± 7 days) until death or study completion. This follow-up may occur through a phone call, email, or visit by the patient or the patient's caretaker.

Refer to [Attachment 1](#) for the Study Schedule.

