6.3.2. Discontinuation of Patients from Study or Study Drug

Patients who are discontinued from the study drug(s) early will have follow-up procedures performed as shown in the Study Schedule ([Attachment 1](#)).

In addition, patients will be discontinued from the study drugs and/or from the study in the following circumstances:

- Enrollment in any other clinical trial involving an investigational product or enrollment in any other type of medical research judged not to be scientifically or medically compatible with this study.
- Investigator/Physician Decision
 - the investigator/physician decides that the patient should be discontinued from the study or study drug(s)
 - if the patient, for any reason, requires treatment with another therapeutic agent that has been demonstrated to be effective for treatment of the study indication, discontinuation from the study drug(s) occurs prior to introduction of the other agent
- Patient Decision
 - the patient or the patient's designee (for example, legal guardian) requests to be discontinued from the study or study drug
- Sponsor Decision
 - Lilly, in consultation with the collaborator, stops the study or stops the patient's participation in the study for medical, safety, regulatory, or other reasons consistent with applicable laws, regulations, and GCP
- The patient has confirmed evidence of progressive disease by RECIST v1.1. In the setting of disease progression, the patient will discontinue from study drug(s); however, the patient will continue to be followed on study. In the setting of unconfirmed/equivocal progression, the patient should remain on study treatment

until the next assessment period or up to 12 weeks after consultation with a Lilly physician. See Section 8.3.1.2 for additional details.

- The patient is noncompliant with study procedures and/or treatment (Section 7.6).
- The patient experiences unacceptable toxicity. Note: If the patient discontinues from 1 study drug, the patient should also discontinue from the other study drug.
- Patient has a dosing interruption of either study drug of >12 weeks.
- The patient becomes pregnant.

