7.2.1. Dosing Schedule

This study defines 1 cycle as 4 weeks or 28 days.

LY2510924 will be self-administered prior to the start of durvalumab infusion on the days both drugs are given together.

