 - a. Any toxicity that is possibly related to study treatment that requires the withdrawal of the patient from the study during Cycle 1 (including Day 15), or
 - b. A delay of >14 days in initiating Cycle 2 due to persistent Grade >2 toxicities
5. Any other \geq Grade 3 toxicity, except for the exclusions listed below.

The definition excludes the following conditions:

- Toxicity that is clearly and directly related to the primary disease or to another etiology is excluded from this definition
- Grade 3 endocrine disorder (thyroid, pituitary, and/or adrenal insufficiency) that is managed with or without systemic corticosteroid therapy and/or hormone replacement therapy and the patient is asymptomatic
- Grade 3 inflammatory reaction attributed to a local antitumor response (for example, inflammatory reaction at sites of metastatic disease, lymph nodes, etc.)
- Concurrent vitiligo or alopecia of any AE grade
- Grade 3 IRR (first occurrence and in the absence of steroid prophylaxis) that resolves within 6 hours with appropriate clinical management
- Grade 3 or 4 neutropenia that is not associated with fever or systemic infection that improves by at least 1 grade within 3 days. Note: Grade 3 or Grade 4 **febrile** neutropenia will be a DLT regardless of duration or reversibility.
- Grade 3 or 4 lymphopenia
- Grade 3 thrombocytopenia that is not associated with bleeding that requires clinically significant medical intervention and improves by at least 1 grade within 3 days
- Isolated Grade 3 electrolyte abnormalities that are not associated with clinical signs or symptoms and are reversed with appropriate maximal medical intervention within 3 days

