8.1. Safety Evaluations

Safety is the primary endpoint of this Phase 1a/b study as determined by the NCI CTCAE v 4.03. All patients who receive at least 1 dose of LY2510924 or durvalumab will be evaluated for safety as measured by the occurrence of AEs, SAEs, deaths, and laboratory abnormalities, assessed during treatment and for 90 days in follow-up.

Patients will have regularly scheduled study visits at the clinical site as noted in [Attachment 1](#), where safety assessments including AE collection, laboratory assessments, vital sign collection, and physical examinations will be performed.

Imaging studies will be performed every 8 weeks or sooner if clinically indicated. Liver function, as part of the routine clinical chemistry panel, will be tested every other week in Cycle 1 and every cycle thereafter.

Study procedures and their timing are described in the Study Schedule ([Attachment 1](#)). [Attachment 2](#) lists the specific tests that will be performed for this study.

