Serum, Plasma, and Whole Blood Samples for Biomarkers		x	See Attachment 4 for exact timing.				x				Baseline sample for whole blood only, and must be collected ≤7 days prior to Cycle 1 Day 1. See Attachment 4 for exact timing.
Radiological Tumor Assessment	x				x		x				Local. CT scans will begin within 7 days prior to starting Cycle 3 and every other cycle afterwards including follow-up (approximately 8 weeks apart).

Relative Day Within a Cycle	Baseline		Cycle 1		Cycle 2	Cycle 3-n	Follow-Up				Comments
	<28 days	<7 days	1	15	1	1	30 day	60 day	90 day	LT FU ^a	
Visits							801	802	803	804	
Blood for pharmacogenetics		x									It is highly recommended to draw the whole blood sample on Cycle 1 Day 1 prior to the first dose; however, it can be collected later during the study if necessary.
Other safety or laboratory assessments; for example, immunogenicity					x	C4			x		Note: Day 1 sample should be taken prior to durvalumab and LY2510924.
Survival/ subsequent anticancer therapy							x	x	x	x	At long-term FUP, at least every 12 weeks ±7days until patient’s death or study completion.
Durvalumab			x		x	x					In clinic on Day 1 of each cycle.
LY2510924			Days 1-28		Days 1-28	Days 1-28					LY2510924 will be self-administered SQ daily. On Cycle 1 Days 1, 2, 15 and 16 and on Cycles 2 to 4 Day 1, LY2510924 should be taken at the clinic (time and date recorded) after a blood sample is taken for LY2510924 PK but prior to the start of durvalumab (refers to Day 1 of each cycle only).
Dispense study drugs and assess compliance			x		x	x					Collect drug diary prior to dispensing study drug for cycle.

Relative Day Within a Cycle	Baseline		Cycle 1		Cycle 2	Cycle 3-n	Follow-Up				Comments
	<28 days	<7 days	1	15	1	1	30 day	60 day	90 day	LT FU ^a	
Visits							801	802	803	804	
Dispense/ collect patient diaries			x		x	x					Patients will complete diaries once per cycle.

Abbreviations: aPTT = activated partial thromboplastin time; C = cycle; CEA = carcinoembryonic antigen; CT = computer tomography; CTCAE = Common Terminology Criteria for Adverse Events; D = day; ECG = electrocardiogram; ECOG = Eastern Cooperative Oncology Group; FUP = follow-up

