**Table CXAD.6.2. Rules for Determining Date of Progression or Censor for Progression-Free Survival**

Rule	Situation	Date of Progression or Censor	Outcome
1	No baseline tumor assessments	Date of first treatment	Censored
2	No postbaseline assessments and no death	Date of first treatment	Censored
3	No documented progression and no death (with a postbaseline tumor assessment)	Date of last adequate tumor assessment	Censored
4	Patient lost to follow-up (or withdrew consent from study participation) before documented progression or death	Date of last adequate tumor assessment	Censored
5	Documented progression	Date of documented progression  If a tumor assessment was done on multiple days, use the earliest date for that visit.	Progressed
6	Death without documented progression	Date of death	Progressed
7	Documented progression or death after missing $\geq 2$ consecutive postbaseline tumor assessments	Date of last adequate tumor assessment before missed assessments or date of first treatment, whichever is later	Censored

Note: Progression-free survival and associated outcome is determined by the earliest of the dates above, if more than 1 situation applies.

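### On-treatment CT is tied to cycle starts in Attachment 1 but to an 8-week interval in the protocol text, with no rule for delayed cycles, so toxicity holds can postpone scans and progression dates

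*Protocol*

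**What the plan says.** The Radiological Tumor Assessment row of Protocol Attachment 1 reads: "CT scans will begin within 7 days prior to starting Cycle 3 and every other cycle afterwards including follow-up (approximately 8 weeks apart". Protocol Section 8.1 states: "Imaging studies will be performed every 8 weeks or sooner if clinically indicated". For patients who stop treatment for reasons other than progression, Protocol Section 6.2 states: "tumor assessments should continue every 8 weeks until confirmed disease progression occurs", or until new anticancer therapy, death or loss to follow-up.

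Cycle length is fixed in Section 7.2.1: "This study defines 1 cycle as 4 weeks or 28 days". Late cycle starts are foreseen: one DLT example in Section 7.2.2.1 is "A delay of >14 days in initiating Cycle 2 due to persistent Grade >2 toxicities". Long interruptions are also foreseen. Section 6.3.2 discontinues treatment only when "Patient has a dosing interruption of either study drug of >12 weeks", and Section 5.2 explains that management of immune-mediated events, "including steroid tapering, allows a 12-week window for resolution before discontinuing study treatment". For several Grade 2 immune-mediated events, Attachment 11 allows treatment to resume only after a steroid taper, which it generally sets at 28 days or more.

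In the SAP, Rule 7 of Table CXAD.6.2 covers progression or death after two or more consecutive missed tumor assessments. The patient is censored at: "Date of last adequate tumor assessment before missed assessments or date of first treatment, whichever is later". The SAP does not define a missed assessment.

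**The concern.** The two anchors coincide only while every cycle starts on time. Once toxicity delays a cycle, a site working from the Attachment 1 grid would wait for the delayed cycle, while a site working from Section 8.1 would scan at 8 weeks. No provision in either document settles this.

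Under the first reading the scan interval depends on toxicity. Patients on hold are looked at less often than those who never needed a hold, and less often than those who stopped treatment and are covered by Section 6.2. Progression is dated at the scan that finds it, so PFS and duration of response would tend to run long in the held patients. Because Rule 7 turns on the number of missed assessments, the same ambiguity could also decide whether a late progression counts as an event. Both measures serve the secondary objective on antitumor activity.

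**Working it through.** **The plan's own figure.** Two cycles of 28 days are 56 days, or 8 weeks. With no delay, the interval stated in Attachment 1 is reproduced and the two anchors agree.

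**Effect of a delay.** If cycle starts slip by h weeks in total within one scan interval, the cycle-timed gap is 8 + h weeks: 10 weeks for h = 2, 12 for h = 4, 16 for h = 8, 18 for h = 10 and 20 for h = 12.

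**Rule 7.** Count the calendar scans (weeks 8, 16, 24 and so on) that fall inside the gap. The documents give no window for the calendar interval, so both strict dates and ±1 week were tried.

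- Delays up to 8 weeks (strict) or 9 weeks (±1 week): at most one calendar scan falls in the gap. Rule 7 is not triggered, and the scan is simply late.
- Longer delays, up to 12 weeks: two fall in the gap. With 12 weeks' delay before Cycle 2 or 3, the first cycle-timed scan is at 8 + 12 = week 20. Progression found there is an event at week 20 if missed scans are counted by cycle (none missed). If they are counted by calendar (weeks 8 and 16 missed), it is censored at first treatment.
- Later in treatment: with the last scan at week 8 and 12 weeks' delay before Cycle 4 or 5, the next scan is at week 28. It gives an event at week 28 by cycle count, or censoring at week 8 by calendar count (weeks 16 and 24 missed).

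Section 6.3.2 does not say when an interruption starts. If the 12 weeks run from the last durvalumab dose, 4 weeks of it are the ordinary dosing interval. The cycle delay is then at most 12 − 4 = 8 weeks, and a single hold does not trigger Rule 7.

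**Size of the shift.** Assumptions, none of them from the documents: exponential time to progression with median m = 8, 12 or 16 weeks, a hold of 6 or 12 weeks before Cycle 3, 10 to 30% of patients held, and all progression found at scheduled scans. Let S(t) = 2^(−t/m). With the first scan at week f and scans every 8 weeks after it, the mean recorded time is f + 8·S(f)/(1 − S(8)). Here f = 8 on the calendar and f = 8 + h after a hold.

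For m = 12, S(8) = 0.630 and S(20) = 0.315.
- Calendar: 8 + 8 × 0.630/0.370 = 21.6 weeks.
- 12-week hold: 20 + 8 × 0.315/0.370 = 26.8 weeks, which is 5.2 weeks later.

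| Median PFS (weeks) | Mean lateness, 6-week hold | Mean lateness, 12-week hold |
|---|---|---|
| 8 | 2.8 weeks | 6.8 weeks |
| 12 | 2.0 weeks | 5.2 weeks |
| 16 | 1.6 weeks | 4.2 weeks |

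These are averages. Some held patients are dated earlier, because their later scans fall between calendar dates. After a 12-week hold, progression between weeks 16 and 20 is found at week 20 instead of week 24.

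**Landmark rates.** At 6 months (week 26) with m = 12, the last calendar scan is week 24, where S = 0.250. After a 12-week hold the last scan is week 20, where S = 0.315. With 20% held, the rate rises by 0.20 × (31.5 − 25.0) = 1.3 points. After a 6-week hold the last scan is week 22 (S = 0.281), and the rise is 0.20 × (28.1 − 25.0) = 0.6 points. Across all settings the rise is 0.2 to 2.0 points.

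At week 12 the same inputs give 0.20 × (100 − 63.0) = 7.4 points (63.0% to 70.4%), and 3 to 15 points across settings. Held patients have no scan until week 14 or 20, so at week 12 all of them count as progression-free by construction.

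**The case against.** The strongest reply is that the calendar interval is already in the plan. Section 8.1 makes no exception for holds and allows earlier scans when clinically indicated. The Synopsis puts the first tumor evaluation at 2 months, and the Attachment 1 line itself says the scans are about 8 weeks apart. A reader might infer that patients on hold will not be scanned every 8 weeks. The documents do not support that as fact, because Section 8.1 covers those patients too. What remains is an anchor left unreconciled, not two rules opposed for every patient.

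A hold also need not move the cycle. Missed LY2510924 doses are not made up (Section 7.2.1.1), and SAP Section 6.8.1 lists dose delays and dose omissions separately. If cycles run on with doses omitted, the Attachment 1 scans stay where they were. Against this, the DLT text does foresee a delayed Cycle 2, so slippage cannot be ruled out.

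Long holds may be uncommon. For Grade 3 or 4 pneumonitis, diarrhea/enterocolitis and nephritis, Attachment 11 calls for permanent discontinuation, which leads to 8-weekly scans under Section 6.2. The documents give no hold frequency. The calculation also leaves out deaths, which Rule 6 dates exactly, and clinically prompted scans; both would shrink the shift.

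Finally, the Rule 7 switch requires scans to follow the cycle while misses are counted by calendar. Either basis used consistently gives no missed scan. This point stands: the defect there is the undefined term.

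**Conclusion.** The point holds as an unreconciled scan anchor with a modest, toxicity-dependent effect on assessment timing. If sites follow Attachment 1 as written, a cycle delay of h weeks makes that scan interval 8 + h weeks. Recorded progression in held patients is then later by a mean of about 1.6 to 2.8 weeks (6-week delay) or 4.2 to 6.8 weeks (12-week delay). This rests on the assumed exponential PFS and on holds before Cycle 3.

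A reader might infer a material inflation of the reported PFS rate. The documents do not support that. At 6 months, the example time point in Protocol Section 10.9, the change is about 0.2 to 2 points with an assumed 10 to 30% held. Larger differences appear only at landmarks between the planned and the delayed scan.

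A reader might also infer that Rule 7 will routinely turn censorings into events. It could do so only for delays above about 8 to 9 weeks within one scan interval, and only if the counting basis differs from the scanning basis.

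PFS and duration of response are descriptive here, with no p-values, so no test or sample size is affected. In an arm of about 15, one reclassified patient is 1/15, or about 7%. The plan's own interval for 9 of 15 already runs from 0.32 to 0.84. The correction is still worth making because it is cheap and removes a dependence of scan timing on toxicity.

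**What to change.** Reconcile Attachment 1 with Sections 8.1 and 6.2 by rewording the Attachment 1 comment along these lines: CT/MRI every 8 weeks (±7 days), counted from Cycle 1 Day 1 regardless of dose delays or interruptions, for as long as the patient is on study treatment, including any treatment beyond progression. After treatment stops without progression, scans continue on the same calendar until one of the endpoints already listed in Section 6.2. The clause on treatment beyond progression is needed because Sections 6.2 and 8.3.1.2 allow it. A rule that ended scans at confirmed progression would leave those patients without an imaging schedule.

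In SAP Table CXAD.6.2, define a missed assessment against that calendar and its window, so that Rule 7 can be applied in only one way.

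The cost is one line in Attachment 1 and one in the SAP. On-treatment scanning is no more frequent than Section 8.1 already states, and no dosing or treatment rule changes. The small downside is that some scans in patients on hold will not coincide with a dosing visit.

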Attachment 2. Protocol CXAD Clinical Laboratory Tests

Clinical Laboratory Tests

Hematology^b

Hemoglobin
Hematocrit
Mean corpuscular hemoglobin
Mean corpuscular hemoglobin concentration
Mean corpuscular volume
Erythrocyte count (RBC)
Leukocytes (WBC)
Neutrophils^c (% and absolute)
Lymphocytes (% and absolute)
Monocytes (% and absolute)
Platelets
Eosinophils
Basophils

Coagulation^b

aPTT
PT
INR

Urinalysis^b

Bilirubin
Blood
Color and appearance
Glucose
Ketones
pH
Protein
Specific gravity
Urine leukocyte esterase

Clinical Chemistry^a

Serum Concentrations of:

Sodium
Magnesium
Chloride
Phosphorus
Potassium
Total and direct bilirubin
Alkaline phosphatase
Alanine aminotransferase
Aspartate aminotransferase
Bicarbonate
Blood urea nitrogen
Creatinine
Total protein
Calcium
Glucose, random
Albumin

Clinical Chemistry^d

Serum Concentrations of:

Lactate dehydrogenase (LDH)
Lipase
Gamma glutamyl transferase (GGT)
Creatine kinase
Amylase

Thyroid Function Tests^b

Thyroid stimulating hormone
Free thyroxine (fT4)

Hepatitis B (HBsAg, Anti-HBc)^b

Hepatitis C (Anti-HCV, HCV RNA)^b

HIV^b

Urine or serum (β -human chorionic gonadotropin
(β -hCG) **Pregnancy Test** (females only)^b

Clinical Laboratory Tests

Abbreviations: aPTT = activated partial thromboplastin time; CRF = case report form; HBsAg = hepatitis B surface antigen; HBc = hepatitis B core antibody; HCV = hepatitis C virus; INR = international normalized ratio of prothrombin time; PT = prothrombin time; RBC = red blood cells; RNA = ribonucleic acid; WBC = white blood cells.

- a Local chemistry laboratory testing will be used to determine patient eligibility and decisions for treatment. Central chemistry laboratory testing will also be performed, and will be used for data analyses.
- b Local or investigator-designated laboratory. Treatment decisions will be based on local laboratory results.
- c Neutrophils reported by automated differential hematology instruments include both segmented and band forms. When a manual differential is needed to report the neutrophils, the segmented and band forms should be added together and recorded on the CRF, unless the CRF specifically provides an entry field for bands.
- d Centrally only.

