7.2.5.1.1. LY2510924 Dose Adjustments and Delays

During Phase 1a, inpatient dose escalation or reduction of LY2510924 is not allowed.

During Phase 1b, 2 dose reductions of LY2510924 are allowed (depending on the starting dose: reduce 1 dose level if available or hold if not available). Reescalation is allowed once at the discretion of the investigator. If Grade 3/4 toxicity attributed to LY2510924 occurs after 2 previous dose reductions, LY2510924 will be discontinued. If patients are discontinued from LY2510924, patients must also be discontinued from durvalumab.

No dose reduction of LY2510924 will occur for myelosuppression. Granulocytosis was observed in patients receiving LY2510924 in the Phase 1 and 2 studies. Management of granulocytosis and nonhematologic toxicity is outlined in [Table CXAD.7.2](#) and in the durvalumab dose-modification tables within [Attachment 11](#).

Table CXAD.7.2. Dose Adjustments of LY2510924

Event	Intervention	Dose Adjustment
Leukocytosis (ANC >75,000/ μ L or leukocytes >100,000/ μ L)	1) Interrupt LY2510924 2) Recheck WBC, ANC every 2 to 3 days until ANC decreases to <50,000/ μ L	Reduce 1 dose level
Injection site reaction, Grade 3	1) Interrupt LY2510924 2) Administer topical treatment as necessary	Reduce 1 dose level
Other nonhematologic toxicities meeting treatment interruption criteria described in Attachment 11	1) Interrupt LY2510924 2) Re-examine patient at least weekly until toxicity improves to \leq Grade 1 and consider restarting treatment according to the durvalumab dose-modification tables (Attachment 11)	Reduce 1 dose level

Abbreviations: ANC = absolute neutrophil cell; WBC = white blood cell.

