8.2.1. Samples for Study Qualification and Health Monitoring

Blood samples will be collected to determine whether patients meet inclusion/ exclusion criteria and to monitor patient health.

Investigators must document their review of each laboratory safety report.

Samples collected for specified laboratory tests will be destroyed within 60 days of receipt of confirmed test results. Tests are run and confirmed promptly whenever scientifically appropriate. When scientific circumstances warrant, however, it is acceptable to retain samples to batch the tests run, or to retain the samples until the end of the study to confirm that the results are valid. Certain samples may be retained for a longer period, if necessary, to comply with applicable laws, regulations, or laboratory certification standards.

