Serum Chemistry and Liver Function Testing		x	x	x	x	x	x	x	x		Local and central. See Attachment 2 . If any abnormalities, will follow beyond the 30-day FUP, as clinically indicated. To include liver enzyme panel.
Tumor Markers in Blood	x		x		x	x	x	x	x		Local. If applicable to tumor type of the patient (eg, CEA in patients with colorectal cancer or CA125 in patients with ovarian cancer). Obtain predose, if dose administered.
Coagulation		x									Local. Includes prothrombin time, aPTT and INR. As clinically indicated on study and prior to any procedures (eg, tumor biopsy).
Thyroid Function Tests		x	x		x	x	x	x	x		Local. Includes TSH and ft4. Additionally, measure if there is clinical suspicion of an adverse event related to the endocrine system.
Urinalysis		x	x		x	x	x	x	x		Local. See Attachment 2 . If any abnormalities, will follow beyond the 90-day FUP, as clinically indicated.
CTCAE v 4.03 Grading		x	x	x	x	x	x	x	x	x	To be reported only after study eligibility is confirmed. Throughout study as needed. Refer to Section 8.1.2.6 for reporting guidelines. Data on SAEs that occur before the end of trial will be stored in the collection database and the Lilly Safety System.
Urine or Serum Pregnancy Test		x									Local. As clinically indicated while on study.

	Baseline		Cycle 1		Cycle 2	Cycle 3-n	Follow-Up				Comments
	<28 days	<7 days	1	15	1	1	30 day	60 day	90 day	LT FU ^a	
Relative Day Within a Cycle	<28 days	<7 days	1	15	1	1	30 day	60 day	90 day	LT FU ^a	Assessments to be performed at the times stipulated in the table and as clinically required in the management of the patient. All assessments to be performed pre-infusion unless stated otherwise.
Visits							801	802	803	804	
Tumor Tissue		≤3 yrs prior			D7						Central. Core or excisional biopsy of a tumor lesion or a recent biopsy defined by ≤3 years since last documented progression of disease. Patients for whom newly obtained samples cannot be obtained such as in cases of inaccessibility or patient safety concern, an archived specimen can be submitted upon agreement from sponsor. If a fresh biopsy is obtained, an archival specimen (if available) should also be submitted for comparison. On-treatment sample (Cycle 2 Day 7 ±7 days): mandatory for ovarian expansion arm (Phase 1b), optional in Phase 1a and pancreatic expansion arm in Phase 1b.
PK Sampling			D1 & 2	D15 & 16	x	C3, C4, & C6			x		See PK Sampling Attachment 4 for exact timing.

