
Grade 2 Hold study drug/study regimen dose until Grade 2 resolution to Grade ≤ 1.
 
If toxicity worsens, then treat as Grade 3 or Grade 4.
 
Study drug/study regimen can be resumed once event stabilizes to Grade ≤ 1 after completion of steroid taper.
 
Patients with endocrinopathies who may require prolonged or continued steroid replacement can be retreated with study drug/study regimen on the following conditions:
 
 1. The event stabilizes and is controlled. 2. The patient is clinically stable as per Investigator or treating physician's clinical judgement. 3. Doses of prednisone are at ≤ 10 mg/day or equivalent. 	

Grade 3 Depending on the individual toxicity, study drug/study regimen may be permanently discontinued. Please refer to guidelines below.
	

Grade 4 Permanently discontinue study drug/study regimen.
	

Note: For Grade ≥ 3 asymptomatic amylase or lipase levels, hold study drug/study regimen, and if complete work up shows no evidence of pancreatitis, study drug/study regimen may be continued or resumed.
	

Note: For Grade 3 and above asymptomatic amylase or lipase levels hold study drug/regimen and if complete work up shows no evidence of pancreatitis, may continue or resume study drug/regimen
	

AE Adverse event; CTC Common Toxicity Criteria; CTCAE Common Terminology Criteria for Adverse Events; irAE Immune-related adverse event; IV intravenous; NCI National Cancer Institute; PO By mouth.

Specific Immune-mediated Reactions

Adverse Events	Severity Grade of the Event (NCI CTCAE version 4.03)	Dose Modifications	Toxicity Management
Pneumonitis/ILD	Any Grade	General Guidance	For Any Grade: 
 – Monitor patients for signs and symptoms of pneumonitis or ILD (new onset or worsening shortness of breath or cough). Patients should be evaluated with imaging and pulmonary function tests, including other diagnostic procedures as described below. – Initial work-up may include clinical evaluation, monitoring of oxygenation via pulse oximetry (resting and exertion), laboratory work-up, and high- resolution CT scan.

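### Lipase and amylase carry a dosing hold but are tested only centrally with no stated turnaround, so unless results are same-day a hold on a Day 1 sample comes after that day's durvalumab

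*Protocol*

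**What the plan says.** **The hold.** The general dose-modification table in protocol Attachment 11 has a note for Grade 3 or higher values: for "asymptomatic amylase or lipase levels, hold study drug/study regimen, and if complete work up shows no evidence of pancreatitis", dosing may then continue or resume.

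**The laboratory.** Attachment 2 puts lipase and amylase in a chemistry panel marked "d Centrally only". The main chemistry panel, which holds AST, ALT, bilirubin and creatinine, carries footnote a: "Local chemistry laboratory testing will be used to determine patient eligibility and decisions for treatment". Hematology carries footnote b: "Treatment decisions will be based on local laboratory results".

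**The timing.** In Attachment 1 the row "Serum Chemistry and Liver Function Testing" falls on Cycle 1 Days 1 and 15 and then on Day 1 of each later cycle. Section 7.2.1.2 gives durvalumab 1500 mg on Day 1 of every cycle. Attachment 1 wants assessments done before the infusion; it does not say that results must be back by then.

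**Turnaround.** Section 8.2.1 says: "Tests are run and confirmed promptly whenever scientifically appropriate". It adds that, where there is a scientific reason, "it is acceptable to retain samples to batch the tests run". No number of hours or days is given, and no alert rule for these enzymes.

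**The concern.** In a patient without symptoms the laboratory value is the only trigger for this hold. It can protect the dosing day only if it is known before dosing. The plan makes local results the basis for treatment decisions and then leaves out two analytes on which one of its own holds depends.

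The protocol does not treat these enzymes as unimportant. Section 8.1.2.3 lists pancreatitis, or laboratory values suggesting it, as a durvalumab event of special interest, and Section 8.1.2.4 asks for rapid communication of such events. Section 7.2.2.1 exempts amylase and lipase only from the rule on Grade 3 values lasting more than 7 days; a Grade 4 laboratory value remains a DLT criterion.

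What is at stake is patient safety on the infusion day. No endpoint or analysis is affected.

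**Working it through.** There is no stated figure to reproduce, so the check compares the documents and counts days.

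**Which laboratory feeds each hold**

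| Analyte with a named threshold that interrupts study drug | Source of threshold | Result used |
|---|---|---|
| AST, ALT, total bilirubin, creatinine | Attachment 11 | Local (footnote a) |
| ANC, leukocytes | Table CXAD.7.2 ("Recheck WBC, ANC every 2 to 3 days until ANC decreases to" a set level) | Local (footnote b) |
| Lipase, amylase | Attachment 11 note | Central only (footnote d) |

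Of 8 such analytes, 6 have a local result and 2 do not.

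**Inputs for the day count**
- Cycle length is 28 days (Section 7.2.1), so the infusions for Cycles 2, 3 and 4 fall on days 1 + 28 = 29, 1 + 56 = 57 and 1 + 84 = 85.
- Draws are on days 1 and 15, then each later Day 1 minus k, where k is the number of days the sample is taken early. As scheduled, k = 0. A value of k = 3 borrows the window that Attachment 1 gives the physical examination.
- T is the central turnaround in days. None is stated, so a range of 1 to 7 is assumed, with T = 0 meaning back before that day's infusion.

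**Formulas.** For an infusion on day D, the result arrives on day D - k + T, so it is in time only if T is no more than k. If it is late, the notice before the next infusion is 28 - (T - k) days.

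| k | T | In time? | Age of newest result at days 29 / 57 / 85 | Notice before next infusion |
|---|---|---|---|---|
| 0 | 0 | Yes | 0 / 0 / 0 days | not needed |
| 0 | 1 to 7 | No | 29 - 15 = 14 / 57 - 29 = 28 / 85 - 57 = 28 | 27 to 21 days |
| 3 | 1 to 3 | Yes | 3 / 3 / 3 | not needed |
| 3 | 4 to 7 | No | 29 - 15 = 14 / 57 - 26 = 31 / 85 - 54 = 31 | 27 to 24 days |

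In each late case one infusion is given before the value is seen. With k = 0, about T further daily LY2510924 doses are also given before a hold can start.

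**Persistence of a dose already given.** Section 5.6 gives a durvalumab half-life of about 21 days. Under simple exponential decline (a simplification), 2^(-28/21) = 0.40, so about 40% of that dose remains 28 days later.

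The documents give no incidence of Grade 3 or higher asymptomatic values, so no number of affected patients is estimated.

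**The case against.** The best reply is that the harm depends on something the documents do not show. Section 8.2.5 names a Central Laboratory Manual, and reporting and alert times may be set there or in a similar document. If results come back the same day, the problem disappears. A reader might infer from Section 8.2.1 that routine safety chemistry is held and batched. The text does not support that: batching is conditional on a scientific reason, and the passage concerns sample retention.

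A reader might also infer that the six local analytes are guaranteed to be known before infusion. They are not. Footnotes a and b make local results the basis for decisions but do not require them before dosing. What stands is that a local result exists for those six and not for lipase and amylase.

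The consequence is also limited. The hold starts a work-up, and dosing may resume if there is no pancreatitis. Patients with symptoms do not depend on this value. After a late result, LY2510924 can be stopped at once and the next infusion held. The Cycle 1 Day 15 sample can inform Cycle 2 Day 1. Section 8.2.1 requires investigators to document review of each laboratory safety report, and Section 8.1.4 has the sponsor's physician review analytes periodically, though neither ties review to the infusion. Section 8.4 treats collection times as targets, and Attachment 1 allows assessments as clinically needed, so a site may draw early or test locally.

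These points reduce the weight of the concern. They do not supply a rule that puts the value in hand before dosing.

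**Conclusion.** The point holds in conditional form. The hold, the central-only testing, the Day 1 draw and the absence of a stated turnaround are all in the text. Whether the hold comes too late for that day's infusion depends on turnaround: it does for every T from 1 to 7 days if the sample is drawn as scheduled, and for T from 4 to 7 if it is drawn 3 days early. The size is one 1500 mg infusion per late result, with 21 to 27 days' notice before the next. The range for T is an assumption. Confidence is medium, and this is a cheap safety improvement that should be made, not a flaw in the design.

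A reader might go further and infer that patients will be infused over known Grade 3 values, or that the protocol has no guidance on pancreatitis. Neither follows. In the late case the value is not yet known. Attachment 11 does promise pancreatic guidance in a table, and the table of specific reactions has no pancreatitis row. But the general table already gives a Grade 2 hold, the enzyme work-up hold and Grade 4 discontinuation. What remains open is only whether immune-mediated Grade 3 symptomatic pancreatitis means a hold or permanent discontinuation. That is a minor separate clarification and does not carry this point.

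**What to change.** 1. In Attachment 2, move lipase and amylase from footnote d to footnote a, so that they are run locally for treatment decisions and centrally for analysis.
2. In the Attachment 1 chemistry row, add: *From Cycle 2, local lipase and amylase results must be reviewed before each durvalumab infusion; the sample may be drawn up to 3 days before Day 1.* This sentence is needed because footnote a alone does not require a result before dosing. The 3 days match the window already given to the physical examination.
3. As a separate clarification in Attachment 11, state whether immune-mediated Grade 3 symptomatic pancreatitis calls for a hold or for permanent discontinuation.

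The cost is two analytes added to a local sample already taken, and a few lines of text. The downsides are a small local laboratory charge, some extra temporary holds for asymptomatic elevations, and sometimes a wait for results on the infusion day or an earlier visit for the blood draw.
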